1.3 Clinical Data to Date

Published data on BP and HR response to Adderall in ADHD patients has yielded conflicting results. While significant research focus has been on the neurocognitive influences of prescription stimulants in ADHD, inconclusive results are reported with regard to changes in vital signs, although they appear to be clinically insignificant. This is mainly due to differences in populations, methodology, dose and duration of administration of stimulants. Studies in children and adolescents suggest that the absolute risk of cardiac events is low, while increased risk for transient ischemic attack, ventricular arrhythmias and sudden death was evident in a few adult studies.¹⁶

Most current evidence is based on research in ADHD children that has not been specifically designed to investigate the cardiovascular effects of stimulants, thus it is difficult to draw definitive conclusions.¹⁷ Furthermore, most studies comment on long-term effects of stimulants in the ADHD population. A 24-hr recording of BP and HR after intake of three different stimulant drugs in children with ADHD, Samuels et al showed statistically, but not clinically significant increase in DBP and HR.¹⁸ Another study performed in ADHD patients, 4-17 years old, showed that only DBP and HR tended to increase with weekly up-titration of daily dose of Adderall from 5 mg to 15 mg. The DBP increased by 3 mmHg and HR increased by 1 beat per minute, while SBP did not change significantly. These changes were thought to be clinically insignificant.¹⁹ Methylphenidate-induced short-long term mean systolic BP changes ranged from +21 to -4 mmHg, while HR ranged from +6 to -13 bpm while short term (around 4 weeks) effects of lisdexamfetamine on systolic BP ranged from +5.4mmHg to -0.8mmHg with HR increases by less than 5bpm²⁰ In another study of more than 220 adults with ADHD the extended release preparation of mixed amphetamine salts (20-60 mg/day) increased BP and HR insignificantly (SBP by 2.3mmHg; DBP by 1.3 mmHg and HR by 2.1 bpm) over 24 months of monitoring.²¹ In adults with ADHD treated for several weeks with amphetamine compounds showed statistically significant increase in SBP (by >5 mmHg) and HR (by >7 bpm).²² Their study also suggested possible inverse relationship between baseline BP and BP response to prescription amphetamine. Adults with relatively lower BP at baseline manifested more change with treatment, suggesting that adults with normal BP may be more susceptible to cardiovascular changes induced by amphetamines.²² Overall, varied results in the ADHD population are likely due to varied lengths of treatment follow up, stimulant dose and type used, age of subjects and comorbidities present. No studies have examined the acute cardiovascular effects of Adderall in Adderall-naïve healthy, young adults who sporadically abuse the stimulant, taking it as a “study-aid”.

We have recently conducted a randomized clinical trial investigating the acute effects of a commercially available energy drink, showing that BP and plasma norepinephrine levels increase strikingly after energy drink intake. The energy drink elicited almost 74% increase in plasma norepinephrine levels, and systolic BP increased by more than 6% after ingestion of one can of energy drink.²³ Amphetamines abused by healthy young people may similarly cause significant hemodynamic changes predisposing them to early cardiovascular events. The acute cardiovascular effects of Adderall when abused intermittently by young people are not known, but could potentially lead to serious health complications, whether used alone or in combination with other stimulants.

1.4 Dose Rationale and Risk/Benefits

We will study the cardiovascular effects of an oral 25 mg dose of generic, short acting, Adderall, as this is the dose commonly misused by young adults. Prior clinical studies in ADHD patients have used Adderall dose in range of 5-15 mg doses per day¹⁹ while others investigating the immediate effects of Adderall did not cite the dose used.¹⁸ Adderall XR has been used in doses ranging from 10-60 mg per day.¹⁷

According to the drug information provided by Lexicomp, the initial recommended oral dosing for adults with ADHD is 5 mg once or twice daily; increasing daily dose in 5 mg increments at weekly intervals until optimal response is obtained; usual maximum dose is 40 mg daily given in

1 to 3 divided doses per day. The recommended initial oral dose of Adderall for adults with narcolepsy is 10 mg daily; increasing daily dose in 10 mg increments at weekly intervals until optimal response is obtained; maximum dose: 60 mg daily given in 1 to 3 divided doses per day. Thus considering the prior clinical research data, we elect to study 25 mg dose of Adderall administered orally, one time dose.

Adderall will be administered orally. Although other forms of Adderall exist, our healthy research participants should have no difficulties with swallowing and oral administration of the medication would be easiest. Design of the placebo drug will also be more effective with oral medication. The drug may be administered without regard to meals. Our study subjects will be fasting prior to initiation of the study.

The following information is taken from Lexicomp, available at Mayo Clinic via UpToDate.

Adverse Reactions Significant: Frequency not always defined.

Cardiovascular: Systolic hypertension (extended release; adolescents: 12% to 35%; dose related; transient), tachycardia (extended release; adults: $\leq 6\%$), palpitations (extended release: 2% to 4%), increased blood pressure, myocardial infarction, Raynaud's phenomenon

Central nervous system: Insomnia (extended release: 12% to 27%), headache (extended release; adults: $\leq 26\%$), emotional lability (extended release: 2% to 9%), anxiety (extended release; adults: 8%), agitation (extended release; adults: $\leq 8\%$), dizziness (extended release: 2% to 7%), nervousness (extended release: 6%), drowsiness (extended release: 2% to 4%), speech disturbance (extended release: 2% to 4%), twitching (extended release: 2% to 4%), aggressive behavior, depression, dysphoria, euphoria, exacerbation of vocal tics, formication, irritability, outbursts of anger, overstimulation, paresthesia, psychosis, restlessness, talkativeness

Dermatologic: Diaphoresis (extended release: 2% to 4%), skin photosensitivity (extended release: 2% to 4%), alopecia, dermatillomania, skin rash, urticaria

Endocrine & metabolic: Weight loss (extended release: 4% to 10%), decreased libido (extended release: 2% to 4%), dysmenorrhea (extended release: 2% to 4%)

Gastrointestinal: Decreased appetite (extended release: 22% to 36%), xerostomia (extended release: 2% to 35%), abdominal pain (extended release: 11% to 14%), nausea (extended release: 2% to 8%), vomiting (extended release: 2% to 7%), diarrhea (extended release: 2% to 6%), constipation (extended release: 2% to 4%), dyspepsia (extended release: 2% to 4%), teeth clenching (extended release: $\leq 4\%$), tooth infection (extended release: $\leq 4\%$), anorexia (extended release: 2%), bruxism, unpleasant taste

Genitourinary: Urinary tract infection (extended release: 5%), impotence (extended release: 2% to 4%), frequent erections, prolonged erections

Hypersensitivity: Anaphylaxis, angioedema, hypersensitivity reaction

Infection: Infection (extended release: 2% to 4%)

Neuromuscular & skeletal: Dyskinesia, rhabdomyolysis, tremor

Ophthalmic: Blurred vision, mydriasis

Respiratory: Dyspnea (extended release: 2% to 4%)

Miscellaneous: Fever (extended release: 5%)

<1% (Limited to important or life-threatening): Cardiomyopathy, cerebrovascular accident, Gilles de la Tourette's syndrome (exacerbation), peripheral vascular disease, seizure, toxic epidermal necrolysis

Warnings/Precautions:

Concerns related to adverse effects:

- Cardiovascular events: [U.S. Boxed Warning]: Use has been associated with serious cardiovascular events including sudden death in patients with preexisting structural cardiac abnormalities or other serious heart problems (sudden death in children and adolescents; sudden death, stroke and MI in adults). These products should be avoided in the patients with known serious structural cardiac abnormalities, cardiomyopathy, serious heart rhythm abnormalities, or other serious cardiac problems that could increase the risk of sudden death that these conditions alone carry. Patients should be carefully evaluated for cardiac disease prior to initiation of therapy. Patients who develop symptoms such as exertional chest pain, unexplained syncope, or other symptoms suggestive of cardiac disease during treatment should undergo a prompt cardiac evaluation.
- CNS effects: Amphetamines may impair the ability to engage in potentially hazardous activities.
- Peripheral vasculopathy: Stimulants are associated with peripheral vasculopathy, including Raynaud's phenomenon; signs/symptoms are usually mild and intermittent, and generally improve with dose reduction or discontinuation. Digital ulceration and/or soft tissue breakdown have been observed rarely; monitor for digital changes during therapy and seek further evaluation (eg, rheumatology) if necessary.
- Visual disturbance: Difficulty in accommodation and blurred vision has been reported with the use of stimulants.

Disease-related concerns:

- Abuse potential: [U.S. Boxed Warning]: Potential for drug dependency exists; prolonged use may lead to drug dependency. Use is contraindicated in patients with history of drug abuse.

Prescriptions should be written for the smallest quantity consistent with good patient care to minimize possibility of overdose.

- Hypertension: Use with caution in patients with hypertension and other cardiovascular conditions that might be exacerbated by increases in BP and HR. Use is contraindicated in patients with moderate to severe hypertension.
- Psychiatric disorders: Use with caution in patients with preexisting psychosis or bipolar disorder (may induce mixed/manic episode). May exacerbate symptoms of behavior and thought disorder in psychotic patients; new onset psychosis or mania may occur with stimulant use; observe for symptoms of aggression and/or hostility. Screen patients with comorbid depressive symptoms prior to initiating treatment to determine if they are at risk for bipolar disorder.
- Seizure disorder: Limited information exists regarding amphetamine use in seizure disorder (Cortese, 2013). The manufacturer recommends use with caution in patients with a history of seizure disorder; may lower seizure threshold leading to new onset or breakthrough seizure activity.
- Tourette syndrome: Use with caution in patients with Tourette syndrome; stimulants may unmask tics.

To minimize the risk of side effects, we elected to use a short acting form of Adderall. Participants will be closely monitored in the CRTU at St Mary's Hospital where medical personnel is available to assist if medical needs were to arise.

2 Study Objectives

Primary Objective

- 1) Determine the hemodynamic changes (magnitude of BP and HR response) in healthy adults after taking one dose of prescription medication Adderall 25 mg orally, one time, and compare these responses to those after a placebo pill

Secondary Objective

- 1) Determine ECG changes and incidence of arrhythmias after consumption of Adderall compared to baseline ECG
- 2) Determine if consumption of a dose of Adderall is associated with altered neurohormonal and cardiovascular activation, assessed by measurements of biomarkers, such as catecholamines before and after Adderall/placebo intake
- 3) Determine if taking Adderall induces orthostatic changes
- 4) Assess baroreflex sensitivity (pace breathing) after Adderall vs placebo intake
- 5) Determine the effect of Adderall on cardiovascular hemodynamics during stress conditions including mental stress (arrhythmics), physical stress (sustained hand grip) and pain stress (cold pressor stress) as compared to measurements at rest
- 6) Determine the changes in heart function and brachial artery reactivity after Adderall intake by using an ultrasound
- 7) Determine the changes in appetite and food consumption after Adderall vs placebo

- 8) Determine the prevalence of stimulant medication use, history of weight changes and dietary habits among healthy adults (utilizing standard questionnaires)

3 Study Design

3.1 General Design

The cardiovascular effects of Adderall, prescription medication often abused by students for non-medical purposes, are not well understood. This is a pilot study to investigate the cardiovascular and metabolic response to taking an oral dose of Adderall (25 mg) by healthy adults. Subjects will be studied using a randomized, double-blind, placebo-controlled, crossover design with two separate experimental sessions: Adderall and placebo pill; studies will be performed on 2 separate study days, each study lasting from 6-8 hours.

[figure not shown]
Active drug: Oral Generic Adderall: total of 25 mg dose. This dose will be compounded by Pharmacy. The compounded dose will contain: [dextroamphetamine sulfate 6.25 mg, dextroamphetamine saccharate 6.25 mg, amphetamine aspartate monohydrate 6.25 mg, amphetamine sulfate 6.25 mg (equivalent to amphetamine base 15.73 mg)].

Placebo drug: Placebo designed by CRTU Research Pharmacist team

Adderall and placebo drug will be prepared by research pharmacists in similar capsule form. Placebo pill is carefully designed by our team of CRTU Research Pharmacists to match the prescription medication, Adderall. Both drugs will be given in an identical manner so that participants and study investigators are not aware of which drug is being administered. Subjects will remain unaware of the nature of the drug administered on each study day throughout the study. Each experimental session (Adderall and placebo pill) will be conducted using the same protocol, in a random order.

Study participants will be recruited and offered participation in this trial as described in other sections of this protocol. Interested qualified participants will be consented. The study will be performed at St Marys CRTU on two separate days minimum 5 days apart. Participants will be consented upon arrival to the CRTU and will be consented by the Research Staff. The start time of the studies will be the same. Participants will be fasting 4 hours prior to the study and will be asked to abstain from all stimulants, including caffeine and alcohol for at least 24 hours prior to initiation of this study. When presenting to the CRTU on the first day of the study, participant's height and weight will be obtained by the CRTU staff. On each study day, CRTU personnel will perform urine pregnancy test if needed. If positive pregnancy test, participant will not be able to participate in the study. The research staff will obtain waist and hip and bioimpedance measurements (described below); the participant, together with the research staff, will fill out several questionnaires regarding cardiovascular health and dietary habits (attached with application). Subsequently, the participants will take part in research studies as outlined below. Baseline measurements will be obtained at rest. After the end of baseline recordings, the subjects will be given 25 mg oral dose of Adderall vs placebo pill. The second set of measurements will be obtained starting 3 hours after taking the pill, using similar protocol as at baseline.

We expect to enroll approximately 25 healthy subjects.

Schematic diagram (flowchart) of study events:

3.2 Primary Study Endpoints

- 1) Determine the hemodynamic changes (magnitude of BP and HR response) in healthy adults after taking one dose of prescription medication Adderall 25 mg orally, one time, and compare these responses to those after a placebo pill

3.3 Secondary Study Endpoints

- 1) Determine ECG changes and incidence of arrhythmias after consumption of Adderall compared to baseline ECG
- 2) Determine if consumption of a dose of Adderall is associated with altered neurohormonal and cardiovascular activation, assessed by measurements of biomarkers, such as catecholamines before and after Adderall/placebo intake
- 3) Determine if taking Adderall induces orthostatic changes
- 4) Assess baroreflex sensitivity (paced breathing) before and after Adderall vs placebo intake
- 5) Determine the effect of Adderall on cardiovascular hemodynamics during stress conditions including mental stress (arrhythmics), physical stress (sustained hand grip) and pain stress (cold pressor stress) as compared to measurements at rest
- 6) Determine the changes in heart function and brachial artery reactivity after Adderall intake using ultrasound
- 7) Determine the changes in appetite and food consumption after Adderall vs placebo
- 8) Determine the prevalence of stimulant medication use, history of weight changes and dietary habits among healthy adults (utilizing standard questionnaires).

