1.1 Background

Increasing number of healthy US students report nonmedical use of prescription stimulants, mainly amphetamines, such as Adderall, to improve their mental focus and academic

performance.²⁻⁵ A University of Kentucky study found that 34% of students used the drugs illegally without prescription during times of high academic stress.⁴ Students report almost immediate increase in attention span, calmer demeanor, greater emotional stability and improvement in school and academic performance.

Amphetamines act by stimulating both the central and autonomic nervous system, increasing the release of neurotransmitters dopamine and norepinephrine at the neuronal synapses, while simultaneously inhibiting their reuptake.⁶ Amphetamines were implemented as a drug to treat ADHD on this basis, suspecting that increased dopamine in the brain would amplify the capacity of children with ADHD to focus on a given task.

The unsupervised, unauthorized abuse and black market sale of Adderall has raised serious public health concerns. The increasing number of young adults who consume a variety of stimulants parallels with an increasing number of emergency department visits due to side effects.²⁻⁴ Case reports have linked prescription amphetamines with development of acute cardiac events such as myocardial infarction, coronary thrombosis, aortic dissection and sudden cardiac death.⁷⁻⁹ Reports of new tachyarrhythmias, cardiomyopathies, and systemic and pulmonary hypertension have also been reported.^{10,11} A joint study conducted by Columbia University and the New York State Psychiatric Institute (per request of the FDA) determined that the odds of sudden death in children between ages 7-19 years old were 7.4 times higher in individuals prescribed ADHD stimulants.⁷ Researchers from the University of Texas Southwestern Medical Center noted a link between amphetamine abuse and occurrence of cardiac arrest, secondary to excessive stimulant consumption, potentially inducing acute inflammatory responses and arterial vasospasms, thus reducing blood supply to the heart muscle.⁸ The mechanisms of these effects however remain unclear.

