Stimulants such as amphetamines and methampethamies have been also increasing recognized to contribute to heat –related illness risk. Several case reports describing possible amphetamine related “heat stress” leading to complicated cardiovascular outcomes.¹²⁻¹⁵ Limited literature is currently available on the effects of stimulants on body’s core temperature and possible risk for stroke.

It is speculated that the adverse events are due to the high sympathomimetic action of stimulants. However, to our knowledge, the mechanisms and magnitude of such hemodynamic responses that may occur with nonmedical use of Adderall in Adderall-naïve, healthy young adults have not been studied in humans in a randomized, double-blind, placebo-controlled fashion.

The acute cardiovascular effects of stimulants in healthy young people are likely to be significant. Considering the increased use of Adderall in adults, these risks may be even higher in people with preexisting cardiac conditions (unidentified hypertension, coronary disease, silent arrhythmias) or in those with a family history of premature heart disease. The goal of the proposed clinical trial is to investigate acute cardiovascular effects of Adderall, administered orally, in healthy, young people not used to amphetamines. We hypothesize that taking an oral dose of Adderall, compared to a placebo pill, increases blood pressure (BP) and heart rate (HR) in Adderall-naïve healthy adults at rest and in response to conditions of mental and physical stress. Furthermore, we hypothesize that these hemodynamic changes are associated with sympathetic activation and

impaired endothelial and cardiac function, which could itself predispose to increased cardiovascular risk. Lastly, we hypothesize that taking an oral dose of Adderall, compared to a placebo pill, alters thermoregulation and acutely suppresses appetite in Adderall-naïve healthy adults.

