4.1 Inclusion Criteria

Target accrual: 30 healthy adults will be recruited for this study.

Subject population: Healthy adults. Subjects will be able to provide written consent to be included in the research study. The inclusion criteria will be verified with the subjects and by review of the Mayo medical documents if available.

Inclusion Criteria:

- 1) Adults 18 years of age and older
- 2) Healthy subjects without known cardiovascular disease, thyroid disease or documented mental health illness
- 3) Subjects who are on no medications that have significant interaction with study drug.
- 4) Subjects with no prior history of regular amphetamine use, and non-prescription stimulants
- 5) Nonsmokers

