4.2 Exclusion Criteria

Exclusion Criteria:

- 1) Subjects with known cardiovascular disease, thyroid disease
- 2) Subjects with history of psychotic disorders/mental health illness, including but not limited to anxiety, depression, bipolar disorder; history of substance abuse or dependence
- 3) Subjects currently taking medications that have significant interaction with study drug.
- 4) Prior history of regular amphetamine use, or non-prescription stimulants
- 5) Smokers
- 6) Pregnant subjects
- 7) Known lactose intolerance (due to presence of lactose in the prepared medication)
- 8) Family history of sudden cardiac death

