4.3 Subject Recruitment, Enrollment and Screening

Study personnel will recruit subjects by word-of-mouth. Study personnel will review whether the subjects meet the inclusion criteria (Section 4.1 of this document), based on review of their available medical records.

Dr. [REDACTED]' lab also keeps a list of prior research participants who were recruited as healthy adults for other research studies and who agreed to be contacted for future studies. Study personnel will review this list and if subjects fulfill the inclusion criteria they will be contacted via the phone, to consider participation in the study (see the attachment: Verbal and Phone Recruitment Script).

Eligible subjects will be thus approached by the study personnel and study will be explained in detail. If subjects show interest in participation, their contact information will be collected and forwarded to study team/study coordinator.

Subjects will sign IRB approved consent form when presenting to the CRTU for the research study. Informed consent may also be obtained via Ptrax digital signature capture technology on Mayo devices.

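### Secondary endpoint 8 claims a prevalence of stimulant use in healthy adults from subjects selected on stimulant use, so the figure would be biased downward by an unknown amount

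*Combined protocol and SAP*

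**What the plan says.** Endpoint 8 appears in the same terms in Section 2 (Study Objectives), Section 3.3 and the endpoint list in Section 7.1: "Determine the prevalence of stimulant medication use, history of weight changes and dietary habits among healthy adults", by questionnaire.

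The eligibility criteria act on the same variable:

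- Section 4.1, inclusion criterion 4: "Subjects with no prior history of regular amphetamine use, and non-prescription stimulants".
- Section 4.2, exclusion criterion 4: "Prior history of regular amphetamine use, or non-prescription stimulants".
- Section 4.2, exclusion criterion 2 also removes people with a "history of substance abuse or dependence".
- Section 1.1 states the goal as studying effects "in healthy, young people not used to amphetamines".

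On sampling, Section 4.3 says "Study personnel will recruit subjects by word-of-mouth" and adds a list of earlier research participants, who are checked against the criteria before they are telephoned. In Section 6.1 consent is step 3 and the Stimulant Intake Questionnaire is step 7. Section 7 gives endpoint 8 no analysis, precision target or caveat of its own; Section 7.2 promises only general descriptive statistics for all variables.

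**The concern.** A prevalence needs a sample whose selection does not depend on the characteristic being counted. Here it does: people with a regular amphetamine history are turned away, and those who remain are asked about stimulant use. The resulting proportion is partly a product of the entry criteria.

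What is at stake is one secondary result. The trial is motivated by widespread non-medical use; Section 1.1 cites a study in which "34% of students used the drugs illegally without prescription during times of high academic stress". A lower proportion, reported under the endpoint's present wording, could be read as evidence about how common such use is in healthy adults, when the design cannot separate that from the effect of eligibility.

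**Working it through.** **No figure to reproduce.** The plan states no expected prevalence, precision or sample size for endpoint 8. The check has two parts: whether any section restores an unselected sample, and how the bias behaves.

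**Part 1: looking for a section that rescues the endpoint.**

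- Is the questionnaire given before eligibility is applied? No. Section 4.3 places the eligibility review at recruitment, and Section 6.1 places the questionnaire after consent.
- Is it given to any group outside the trial? No section says so.
- Is endpoint 8 limited to eligible or enrolled subjects? Not in Sections 2, 3.3 or 7.1.
- Is there a sampling frame? No. Section 4.3 describes a convenience sample.

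**Part 2: direction and size.**

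Inputs:

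- p, the true prevalence of any use in the pool from which subjects are drawn. The documents do not give it. The 34% in Section 1.1 is the only non-medical use rate available. It comes from students at one university in periods of academic stress, so it serves as an illustration and not as a benchmark for adults aged 18 and older. A second, assumed value of 10% is shown beside it.
- r, the share of users removed by eligibility. The documents do not give it, so it runs from 0 to 1. Criteria unrelated to stimulant use are assumed to remove users and non-users alike.

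Out of the pool, p(1 − r) users and 1 − p non-users remain, so the total remaining is 1 − pr:

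observed prevalence = p(1 − r) / (1 − pr)

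The shortfall is p − p(1 − r)/(1 − pr) = pr(1 − p)/(1 − pr). This is positive whenever r > 0 and 0 < p < 1, so the direction is downward whatever the value of r.

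For p = 0.34:

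- r = 0.25: 0.255 / 0.915 = 27.9%
- r = 0.5: 0.170 / 0.830 = 20.5%
- r = 0.75: 0.085 / 0.745 = 11.4%
- r = 1: 0 / 0.660 = 0%

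| r | Observed, p = 34% | Expected users in 30 subjects, p = 34% | Observed, p = 10% (assumed) |
|---|---|---|---|
| 0 | 34.0% | 10.2 | 10.0% |
| 0.25 | 27.9% | 8.4 | 7.7% |
| 0.5 | 20.5% | 6.1 | 5.3% |
| 0.75 | 11.4% | 3.4 | 2.7% |
| 1 | 0% | 0 | 0% |

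The counts are 30 (the target in Section 4.1) times the observed prevalence at p = 34%. The table covers only the effect of the criteria. Word-of-mouth recruitment adds a further error whose direction is unknown.

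**The case against.** **Sporadic users are not excluded.** For amphetamines the criterion concerns regular use. Sections 1 and 1.3 treat people who take Adderall sporadically as Adderall-naïve, so such a person can be eligible and the questionnaire can record use. It is also unclear whether the word for regularity extends to non-prescription stimulants, and what that phrase covers. This stands. A reader might infer that the criteria drive the estimate to zero, or that they conceal nearly all of the cited 34%. The documents do not support that: it is the r = 1 end of the table, and the 34% describes use at stressful times, which is not shown to be regular.

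**The other criteria reach less far than they seem.** Exclusion 3, "Subjects currently taking medications that have significant interaction with study drug", concerns current interacting medication. It does not name stimulants and does not remove past use, so it adds little. Exclusion 2 removes abuse or dependence, not any use. Both points stand.

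**Confidence limits do not measure this bias.** One might point to 0 of 30 users, with an exact 95% upper limit of 11.6%, as showing how far the result would fall below 34%. That limit describes sampling precision. An unselected sample of 30 with no users would give the same limit, so it says nothing about the size of the selection effect.

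**The plan would only produce a descriptive table.** The protocol uses healthy adults as the label for its own subjects, calls itself a pilot, and plans no inference for endpoint 8. A reader might nevertheless infer that following the plan must lead to a wrong conclusion. That goes too far, since the error arises when the proportion is reported as a prevalence. But that is what the endpoint asks for in three places, and no section withdraws the claim. This argument lowers the severity without removing the point.

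**Two of the three components are not truncated.** Weight history and dietary habits are not filtered by criterion 4. They share only the ordinary limits of a small convenience sample. This stands.

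**Conclusion.** Wrong as written, at minor severity. Endpoint 8 names a population prevalence, while the eligibility criteria select on prior stimulant use and the questionnaire reaches only people who have passed them. The stimulant-use proportion would be biased downward for any r above 0, but need not be zero. Its size cannot be computed from the documents. At an illustrative true rate of 34%, the observed rate would lie anywhere from just under 34% to 0%, with 20.5% if half of users are removed.

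This rests on two assumptions: eligibility removes at least some users, which is the evident purpose of criterion 4, and the remaining criteria do not remove non-users in greater proportion. The conclusion does not extend to weight history or diet as a truncation problem, and it does not touch the randomised comparison of blood pressure and heart rate.

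**What to change.** Restate endpoint 8 in Sections 2, 3.3 and 7.1 along these lines:

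> *Describe prior stimulant exposure, weight history and dietary habits in the enrolled subjects, as baseline characteristics. Because eligibility excluded regular amphetamine users and people with a history of non-prescription stimulants, these figures do not estimate prevalence in healthy adults.*

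Report the item with the other baseline characteristics under the descriptive statistics in Section 7.2, and say in the same place whether the regularity qualifier applies to non-prescription stimulants, so that readers know which users were removed.

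The cost is wording in three places and the loss of one secondary claim that the design cannot support. The questionnaire, visits, sample size and primary analysis do not change. Giving the questionnaire to everyone approached, before eligibility is applied, would remove the truncation but not the convenience sampling. It would add work and still not give a population prevalence.
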